#### 7.4.6. Post-Operative

After hemostasis is achieved and confirmed at the required intervals, the access site should be monitored every 15 minutes for the first hour for all subjects.

Post-procedure, record the following information:

- **P2 TIME:** Record the date and time the subject was able to ambulate 20 feet without venous re-bleeding from the access sites.
- **P3 TIME:** Record the date and time the subject was eligible for discharge, based solely on the assessment of the access site, as determined by the medical team (i.e., absence of access site bleeding or obvious complications).
- **P4 TIME:** Record the date and time the subject was discharged from the facility.
- Any medication administered for management of pain or anxiety while the subject is on bedrest will be collected.

#### **Ambulation Guidelines by treatment arm:**

Time to Ambulation is the primary efficacy endpoint of the study, therefore every effort must be made to ambulate the subjects within the timelines described below, providing that the subject is medically stable to do so.

#### **Cardiva Mid-Bore VVCS:**

Bed rest for 2 hour minimum to a 2.5 hour maximum, then ambulate if stable. Check groin immediately post ambulation. Re-check groin after 15 minutes to verify status. Any ambulation delay beyond 3 hours final access site hemostasis time that is not related to a medical condition (e.g., pt. is sleeping, no staff available) will be documented, and a Protocol Deviation will be written. NOTE: If one or more of the access sites are not able to be closed with the Mid-Bore VVCS (e.g., complication preventing use of the device, user error), subjects should be maintained on bedrest according to the Investigator's discretion and all study times will be collected. This would not constitute a deviation from the protocol.

#### **Manual Compression:**

Follow institutional guidelines for ambulation. Check groin immediately post ambulation. Re-check groin after 15 minutes to verify status. Any delays of > 30 minutes beyond institution's standard practice for ambulation that are not related to a medical condition (e.g., pt. is sleeping, no staff available) will be documented, and a Protocol Deviation will be written.

#### **Time to Discharge Eligibility Guidelines (all subjects):**

Approximately 15 (+/- 5) minutes after the subject has successfully completed the ambulation assessment (P2), all access sites should be carefully assessed for the following:

- Forming or expanding hematoma
- Presence of any obvious vascular complications at the access site.

If the subject does not exhibit any of these symptoms at any of the access sites, he/she may be considered to be "Eligible for Hospital Discharge" based on this study definition of the access site assessment only. These are basic guidelines for this study-required assessment only, and are not intended to impact actual hospital discharge times for these subjects. Using these guidelines, the Investigator may delegate this TTDE assessment to qualified medical personnel.

Any significant delay in determination of this discharge eligibility (i.e., > 30 minutes after successful ambulation) that is not related to the access site assessment will be documented as a protocol deviation (e.g., no staff available, other condition unrelated to access site).

**NOTE:** If there is any sign of active bleeding at the access site(s) after ambulation, measures should be taken to re-achieve hemostasis and then the subject re-ambulated when the Investigator determines that it is appropriate to do so. In these cases, TTA and TTDE will be repeated and documented when successful, and the re-bleeding will be documented as an adverse event.

#### **Patient Experience Survey Administration Guidelines [Attachment 4]**

All subjects will be given a Patient Experience Survey to complete after successful TTA, at the time of TTDE to characterize their experience while on bedrest post-procedure. The Research designee should give it to the patient, according to the Instructions provide in the Manual of Operations. The completed Survey should be collected at the time of completion. These data will be entered in the eCRF but will not be included in endpoint analyses or hypothesis testing.

#### **Time to Discharge Guidelines (all subjects):**

Prior to hospital discharge, all subjects will be asked about any lower extremity nerve complaints in both lower limbs (i.e., symptoms, severity) that were not existing prior to the index procedure. The data will be captured in the Case Report Forms.

Research personnel should attempt to confirm a date for a follow-up visit at 30 (+/-7) days with the subject prior to discharge to ensure compliance. Ultrasound sub-study subjects should have their ultrasound appointments scheduled to ensure compliance.

#### **Documentation of Venous Re-Bleeding at Femoral Access Site:**

If a subject experiences venous re-bleeding at any of the femoral venous access sites after a) hemostasis had been confirmed for at least 5 minutes and b) prior to hospital discharge, document the following information on the Discharge eCRF:

- Location of bleed (indicate right or left groin);
- Date and time of re-bleed;
- Complete adverse event form.

## **7.5. Follow-up at 30 (+/- 7) Days**

Subjects should be present for an in-person office visit  $30 \pm 7$  days following their index procedure. The subject should be queried regarding any complications they experienced after hospital discharge and the status of the access site wounds should be assessed. All subjects will be asked about any lower extremity nerve complaints in both lower limbs (i.e., symptoms, severity) that were not existing prior to the index procedure. These data will be captured in the Case Report Forms.

If a subject cannot attend an office visit for any reason, a telephone follow-up should be completed for safety assessment, however this will be documented as a protocol deviation and the subject's follow-up will be considered incomplete. These subjects will not be withdrawn.

At select sites, a subset of 25 subjects from each treatment arm will have an ultrasound exam of the bilateral femoral access sites performed and a digital image recorded for each limb.

## **7.6. Study Exit**

Once the subject has completed the follow-up visit or has withdrawn, they should be exited from the study provided they do not have any conditions that require continued follow-up. The date of exit and subject status should be recorded on the Study Exit CRF.

# **8. Assessment of Effectiveness and Safety**

## **8.1. Primary Effectiveness Endpoint**

**Time to ambulation (TTA):** defined as elapsed time between removal of the final Mid-Bore VVCS device (treatment arm) or removal of the final sheath (control arm), and time when subject stands and walks 20 feet without evidence of venous re-bleeding from the femoral access sites (**Per-patient analysis**).

TTA will be reported in hour (hh): minutes (mm).

## **8.2. Secondary Effectiveness Endpoints**

**Time to discharge eligibility (TTDE),** defined as elapsed time between removal of the final Mid-Bore VVCS device (treatment arm) or removal of the final sheath (control arm), and when subject is eligible for discharge based solely on the assessment of the access site, as determined by the medical team. (**Per-patient analysis**).

TTDE will be reported in hour (hh): minutes (mm).

**Time to discharge (TTD),** defined as elapsed time between removal of the final Mid-Bore VVCS (treatment arm) or removal of the final sheath (control arm), and when subject is discharged from the institution. (**Per-patient analysis**).

TTD will be reported in hour (hh): minutes (mm).

### **Procedural Endpoints:**

- **Time to Closure Eligibility (TTCE):** defined as elapsed time between removal of the last procedural device/catheter for the index procedure and the removal of the first Mid-Bore

VVCS device (treatment arm) or removal of the first sheath (control arm).  
**(Per patient analysis).**

*TTCE will be reported in minutes (hh:mm).*

- **Time to hemostasis (TTH)**, defined as elapsed time between removal of the Mid-Bore VVCS device (treatment arm) or removal of the sheath (control arm), and first observed and confirmed venous hemostasis, for each access site. **(Per-access site analysis)**

*TTH will be reported in minutes (mm): seconds (ss).*

**Total Post-Procedure Time (TPPT):** defined as elapsed time between removal of the last procedural device/catheter for the index procedure and when subject is able to successfully ambulate. **(Per-patient analysis)**

*TPPT will be reported in hour (hh): minutes (mm).*

**Procedure Success**, defined as attainment of final hemostasis at all venous access sites and freedom from major venous access site closure-related complications through 30 days  
**(Per-patient analysis, both arms).**

**Device Success**, defined as the ability to deploy the delivery system, deliver the collagen, and achieve hemostasis with the Mid-Bore VVCS.

**(Per-access site analysis, treatment arm only).**

See Table 4 for additional time and endpoint details.

**Table 4: Study-required Data Collection and Endpoint Calculations**

Time Point	Reported Units	Procedure Step	TTCE	TTH	TTA	TTDE	TTD	TPPT
P0	hh:mm	Index Procedure: First procedure sheath inserted						
P1	hh:mm	Index Procedure: Final Device/Catheter removed from sheath						
-	-	Final Sheath Exchange, as applicable						
T1.1	hh:mm:ss	Access Site 1 - start hemostasis*			T1.2-T1.1			P2-P1
T1.2		Access Site 1 - confirmed hemostasis						
T2.1		Access Site 2 - start hemostasis*			T2.2-T2.1			
T2.2		Access Site 2 - confirmed hemostasis						
T3.1		Access Site 3 - start hemostasis*			T3.2-T3.1			
T3.2		Access Site 3 - confirmed hemostasis						
T4.1		Access Site 4 - as applicable start hemostasis*			T4.2-T4.1	P2-TX.1	P3-TX.1	
T4.2		Access Site 4 - confirmed hemostasis						
P2	hh:mm	Ambulation					P4-TX.1	
P3		Discharge Eligibility - per medical team						
P4		Discharge						
		*Where "start hemostasis" is: Treatment: VVCS removal Control: Sheath removal				Where "X" is final access site for the patient, shown here aligned with access site 4 for simplicity.		

hh: hours; mm: minutes; ss: seconds

**Endpoint Abbreviations:**

- TTCE: Time to Closure Eligibility
- TTH: Time to Hemostasis
- TTA: Time to Ambulation (primary)
- TTDE: Time to Discharge Eligibility
- TTD: Time to Discharge
- TPPT: Total Post Procedure Time

### **8.3. Primary Safety Endpoint**

On a **per-limb basis**, the rate of combined major venous access site closure-related complications through 30 days post-procedure, attributed directly to the closure method (i.e., “device-related” with no other likely attributable cause):

- Access site-related bleeding requiring transfusion;
- Vascular injury requiring surgical repair;
- Access site-related infection confirmed by culture and sensitivity, requiring intravenous antibiotics and/or extended hospitalization;
- New onset permanent access site-related nerve injury (i.e., persisting for > 30 days)
- New onset access site-related nerve injury in the ipsilateral lower extremity requiring surgical repair;
- Pulmonary embolism requiring surgical or endovascular intervention and/or resulting in death, to be confirmed by CT pulmonary angiography, lung ventilation/perfusion scan (VQ scan) or autopsy;
- Pulmonary embolism NOT requiring surgical or endovascular intervention and/or NOT resulting in death, to be confirmed by CT pulmonary angiography or lung ventilation/perfusion scan (VQ scan).

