### **7.4.2. Intra-Operative – Data Collection for All Subjects**

For consented subjects that continue to meet the Pre-operative Eligibility Criteria, record the following data regarding their procedure:

- procedure type: A-Fib, Other
  - If A-Fib, record: paroxysmal, persistent, and chronic / permanent, other
- ablation modality (e.g., RF, Cryo)
- **P0 TIME:** time of first index procedure sheath insertion
- number and location of access site locations (3 or 4)
- techniques used to gain venous access, if any (e.g., ultrasound, micropuncture)
- procedural anti-coagulation administered
- final procedural ACT time and value
- protamine administration, dose and time (if given)
- time of extubation

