## **13. Adverse Events**

### **13.1. General**

All adverse events (AE) and serious adverse events (SAE) will be monitored from the time of randomization through the 1-month follow-up visit.

An AE is defined as any undesirable clinical occurrence in a patient whether or not it is considered to be device related. In addition, the definition of AE applies to any event with an onset post study procedure or to any underlying diseases present at baseline, that exacerbate in severity post study procedure. Therefore, an underlying disease that was present at the time of enrollment is not reported as an AE, but any increase in the severity of the underlying disease is to be reported as an AE. This definition includes events occurring during the follow-up period.

All reported AEs must be recorded in the electronic database. A description of the event, including the start date, resolution date, action taken, and the outcome should be provided, along with the Investigator's assessment of the relationship between the AE, the study treatment and the study procedure.

The following definitions for rating severity of adverse events will be used:

Mild:	Awareness of signs or symptoms, but easily tolerated; are of minor irritant type; causing no loss of time from normal activities; symptoms would not require medication or a medical evaluation; signs or symptoms are transient.
Moderate:	Interferes with the subject's usual activity and/or requires symptomatic treatment.
Severe:	Symptom(s) causing severe discomfort and significant impact of the subject's usual activity and requires treatment.

A serious adverse event (SAE) is defined as an event which leads to:

- Death due to any cause
- Life-threatening condition
- Results in persistent or significant disability/incapacity
- Requires in-patient hospitalization or prolonged hospitalization
- Results in congenital abnormality

All SAE's will be reported.

**Device-Related Adverse Event:** an adverse event is considered to be device-related when, in the judgment of the Investigator, the clinical event has a reasonable time sequence associated with use of the investigational device and is unlikely to be attributed to concurrent disease or other procedures or medications. It is reasonable to believe that the device directly caused or contributed to the adverse event.

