**Procedure-Related Adverse Event:** an adverse event is considered to be procedure-related when, in the judgment of the Investigator, it is reasonable to believe that the event is associated with the assigned study procedure and is not specific to the investigational device used. Other products, surgical techniques, or medications required specifically for the procedure are likely to have contributed to the occurrence of the event.

**Concomitant Medication-Related Adverse Event:** an adverse event is considered to be concomitant medication related when, in the judgment of the Investigator, it is reasonable to believe that the event is associated with concomitant medications used in conjunction with the investigational device and is not otherwise specific to the investigational device (e.g. bleeding associated with anticoagulation medication).

**Pre-Existing Condition-Related Adverse Event:** an adverse event is considered to be related to a pre-existing condition when, in the judgment of the Investigator, it is reasonable to believe that the event is associated with the subject's pre-existing condition and is not specific to the investigational device or procedure. Pre-existing conditions that are aggravated or become more severe during or after the procedure should be evaluated on a case-by-case basis to determine if the event may be more appropriately classified as device-related or procedure-related.

Cardiva Medical, Inc., or its designee, in cooperation with the Investigator, will assess all adverse events considered to be device-related for potential reportability to the FDA and other regulatory authorities as an Unanticipated Adverse Device Effect (UADE).

The Investigator should follow all unresolved serious adverse events until the events are resolved, the subject is lost to follow-up, the subject has withdrawn consent, or the adverse event is otherwise explained.

**Non-Events:** For purposes of this study, the following events are not considered adverse events, because they are normally expected to occur in conjunction with catheter-based procedures / post-procedure, or are associated with customary, standard care of subjects undergoing these procedures:

- Early post-operative pain (within 24 hours post-index procedure) at the access site and/or related to position on procedure table
- Post-anesthesia/conscious sedation emesis, nausea, or headache (within 24 hours post-index procedure)
- Chest pain without associated ECG changes

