## **14. Study Committee**

### **14.1. Data Safety Monitoring Committee (DSMC)**

An independent combination Clinical Events Committee (CEC) and Data Safety Monitoring Board (DSMB), referred to as the Data Safety Monitoring Committee, or DSMC, shall be responsible for systematic review and adjudication of all reported major and minor access site-closure related endpoint complications. All other events reported to be potentially device- or procedure-related by the Investigator will be reviewed by an independent Safety Manager and/or a member of the DSMC to determine whether it meets criteria for adjudication. In order to enhance objectivity and reduce the potential for bias, the DSMC members shall be independent of the Sponsor as well as the investigational sites/ Investigators.

Members shall consist of at least two (2) independent physicians with experience in catheter-based procedures, and a statistician. A third independent physician may be utilized in cases when disparity occurs between the two primary DSMC reviewers.

The methodology for performing these responsibilities shall be developed and outlined in the Adjudication Charter. Operational provisions shall be established to minimize potential bias.

The DSMC may recommend study termination if safety concerns warrant such action. The DSMC will establish guideline criteria for recommending study termination, to the extent that it is possible for the DSMC to predict adverse events or outcomes, before the proposed study begins.

The Safety Manager will maintain contact with the DSMC members to schedule event reviews in order to assure close and timely monitoring of adverse events and outcomes.

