### **ACCESS SITE-RELATED BLEEDING REQUIRING TRANSFUSION (major safety endpoint)**

Bleeding originating from the venous access site(s), which has occurred to the degree that transfusion of blood products is necessary to maintain hemodynamic stability.

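### The primary safety test depends on causal attribution by an investigator who knows the arm, and no non-inferiority analysis without that filter is planned

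*Combined protocol and SAP*

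**What the plan says.** **Endpoint.** Section 8.3, like the synopsis, limits the primary per-limb rate to major complications attributed directly to the closure method. It glosses this as device-related "with no other likely attributable cause".

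**Causality rules.** Under section 13.1 an event is device-related when, in the investigator's judgment, it is plausibly timed and "is unlikely to be attributed to concurrent disease or other procedures or medications". The same section's example of a concomitant-medication-related event is "bleeding associated with anticoagulation medication". Section 7.4.2 records "procedural anti-coagulation administered" for every subject. Anticoagulation is not an exclusion, apart from low molecular weight heparin within 8 hours of the procedure.

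**Component definition.** Section 19.2 defines the major bleeding component as "Bleeding originating from the venous access site(s), which has occurred to the degree that transfusion of blood products is necessary" to maintain hemodynamic stability. It has no rule for a bleed to which a drug contributed.

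**Adjudication.** Under section 14.1 the DSMC "shall be responsible for systematic review and adjudication of all reported major and minor access site-closure related endpoint complications". For the rest, "All other events reported to be potentially device- or procedure-related by the Investigator will be reviewed by an independent Safety Manager" and/or a DSMC member, who decides whether adjudication is needed. The DSMC entry in section 19.2 is wider: all reported deaths and all major and minor vascular complications, with no condition on the investigator's attribution.

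**Analysis.** Section 9.2.3 tests the attributed rate against a 5-point margin and summarizes all adverse events descriptively, whatever their relationship to closure. The sensitivity analyses in section 9.1.3 concern missing data only.

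**The concern.** The component definitions already require an access-site origin or, for pulmonary embolism, imaging or autopsy confirmation. The attribution clause is a second filter on top of them, and it is applied first by someone who knows which closure method was used. A transfused groin bleed in an anticoagulated patient has a route out of the primary count in the protocol's own causality definitions.

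This matters more in a non-inferiority test with a fixed absolute margin than in a superiority test. If genuine closure-caused events are removed in the same proportion from both arms, the observed difference and its variance both shrink, and an unacceptable device passes more easily. Removal at different rates in the two arms can push the result either way. Few events are expected, so a single reattribution can settle the outcome.

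**Working it through.** **Inputs.** There are 204 limbs per arm (102 subjects × 2 limbs; section 9.3 gives 204 per arm and calls them patients). The margin is 5 points, tested by the upper limit of a two-sided 95% interval, and the planning rate is 2% per limb in both arms (sections 9.2.3 and 9.3). The fractions of events lost to attribution are my assumptions, because the documents give none. I use the Newcombe limit, which section 9.3 adopts as its approximation to the planned bootstrap.

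**Formulas.** Wilson limits for x/n with p = x/n and z = 1.96:

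l, u = [p + z²/2n ± z√(p(1−p)/n + z²/4n²)] / (1 + z²/n)

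Newcombe upper limit: U = p₁ − p₂ + √[(u₁ − p₁)² + (p₂ − l₂)²]

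Pass probability: the sum of Bin(x₁; 204, p₁) × Bin(x₂; 204, p₂) over all pairs with U < 0.05.

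**Step 1: the plan's own figures.**
- 6/204 vs 4/204: U = 0.0098 + √(0.0333² + 0.0120²) = 0.045, a pass, as in the section 9.2.3 example.
- 7/204 vs 4/204: U = 0.0147 + √(0.0348² + 0.0120²) = 0.052, a fail. On this limit one event decides the result.
- Power at 2% vs 2%: 0.877, against the stated 0.88.

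**Step 2: equal loss of truly closure-caused events, at a true difference equal to the margin (6% vs 1%).** The retained fraction is f = 1 − (share of events at risk) × (share of those lost).

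| Assumed loss | f | Rates tested | False-pass probability |
|---|---|---|---|
| None | 1 | 6.00% vs 1.00% | 0.021 |
| Bleeds 1/7 of events, half lost | 13/14 | 5.57% vs 0.93% | 0.033 |
| Bleeds 1/3 of events, half lost | 5/6 | 5.00% vs 0.83% | 0.057 |
| 25% of all events lost | 0.75 | 4.50% vs 0.75% | 0.090 |
| 50% of all events lost | 0.50 | 3.00% vs 0.50% | 0.32 |

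**Step 3: unequal loss (true rates 7% vs 2%, baseline 0.023).** Losing 20% of device-arm events only gives 0.096. Losing 25% or 50% of control events only gives 0.012 or 0.006, so the direction reverses.

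**Step 4: lost events that are background, equally frequent in both arms.** Closure-caused rates of 5% vs 0% give 0.023 when only those events count. Adding 1% or 2% background to each arm and counting everything (6% vs 1%, 7% vs 2%) gives 0.021 or 0.023. Filtering out background does not inflate the error.

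**Step 5: power of an attribution-free analysis.** If counting everything raised both rates from 2% to 3%, power would fall from 0.88 to 0.77.

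**The case against.** A reader might infer that the endpoint is biased toward non-inferiority, with false-pass rates of 0.3 to 0.4. The documents do not support that. The 0.32 in the last row of the table, and the 0.42 obtained at 5% vs 0%, both require half of all seven major components to be lost. The anticoagulation route concerns bleeding; it is not an evident alternative explanation for infection, nerve injury or pulmonary embolism. Both figures also assume that every lost event was truly closure-caused. Step 4 shows no inflation otherwise, and step 3 shows that the direction is not fixed.

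A reader might also infer that such bleeds escape adjudication altogether. That too goes beyond the text. Section 13.1 classes an event as procedure-related where medications required for the procedure probably contributed. A bleed blamed on procedural anticoagulation can therefore reach screening under section 14.1, whose threshold is only potential relatedness. Section 19.2 gives the committee a wider remit still, and section 13.1 recognizes contribution by the device as well as sole causation. The gap is partial, and arises where the two descriptions of the remit diverge.

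Nor do the documents show that control events cannot count. Section 13.1 ties device-relatedness to the investigational device, but section 8.3's operative phrase is the closure method, and sections 9.2.3 and 9.3 plan for control-arm events.

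Attribution to the closure method is also a legitimate pre-specified choice of endpoint, and filtered events would remain visible in the adverse-event summaries. All of this stands. It leaves three things unanswered: the first attribution is made with knowledge of the arm, adjudication is not stated to be blinded (section 14.1 promises only unspecified provisions against bias), and no tested analysis shows whether the conclusion depends on the filter.

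**Conclusion.** The concern holds as a dependence of the primary safety test on attribution that the plan neither controls fully nor examines. It does not hold as a demonstrated bias in one direction. Under equal loss of truly closure-caused events at 6% vs 1%, the false-pass probability rises from 0.021 to roughly 0.03–0.06 when only some bleeds are lost, and to 0.09 when a quarter of all events are lost. It falls if mainly control events are lost and is essentially unchanged if the lost events are common background.

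These figures rest on assumed loss fractions, independent limbs and the Newcombe approximation; the patient-level bootstrap would give somewhat different values. Because one event can decide the result and the remedy is cheap, the change should be made. Confidence is moderate, because the true attribution rate is unknown.

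**What to change.** 1. Keep the attributed rate as the primary safety endpoint.
2. Align section 14.1 with the DSMC entry in section 19.2, and carry this into the Adjudication Charter: the committee adjudicates every access-site, limb or pulmonary embolism event that meets a major-component definition, whatever the investigator's attribution. State whether adjudicators are blinded to arm.
3. In section 9.2.3, pre-specify a supportive analysis of all adjudicated major access-site events regardless of attribution, with the same patient-level bootstrap and the same 5-point margin.
4. In section 8.3 and the synopsis, replace device-related with closure-method-related, in either arm.

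The cost is protocol, analysis-plan and charter wording plus a few extra adjudications, with no added subjects or visits. All-event rates will be somewhat higher than attributed rates, and the supportive analysis will have less power (for example 0.77 at 3% vs 3%, against 0.88 at 2% vs 2%). It should therefore inform interpretation and not become a second success criterion.
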